## 8.6. Pharmacokinetics

Pharmacokinetic parameters are not evaluated in this study.

# 8.7. Genetics and/or Pharmacogenomics

Genetics and/or pharmacogenomics are not evaluated in this study.

# 8.8. Biomarkers

Neurophysiologic biomarkers being evaluated in this study include fMRI (Section 8.2.3.2).

# 8.9. Immunogenicity Assessments

Immunogenicity assessments are not evaluated in this study.

# **8.10.** Medical Resource Utilization and Health Economics

Medical Resource Utilization and Health Economics parameters are not evaluated in this study.

CONFIDENTIAL 54 27 February, 2024

## 9. Statistical Considerations

# 9.1. Statistical Hypotheses

The objective of this study is to evaluate the safety of oral TRP-8802 in concert with psychotherapy among adult participants with FM. Based on previous studies with psilocybin in other conditions (Davis 2021a, Carhart-Harris 2016), it is hypothesized that oral TRP-8802 in concert with psychotherapy will be safe and well-tolerated among participants with FM.

# 9.2. Sample Size Justification

The study is intended to gather preliminary evidence of safety of TRYP-8802 in conjunction with psychotherapy in participants with FM, and to help inform future clinical studies. As this is a pilot study, the sample size was selected based on previous pilot studies of psilocybin-assisted therapy in other conditions (e.g., major depression disorder) (Davis 2021a, Carhart-Harris 2016). Accordingly, for this pilot, proof-of-concept study, participants will be screened with the goal of enrolling approximately 10 participants who will complete both doses of TRP-8802 and the primary and secondary outcome measures, and complete the study and follow-up periods.

Note: "Enrolled" means a participant's agreement to participate in the clinical study following completion of the informed consent process and all screening assessments successfully. Potential participants who are screened for the purpose of determining eligibility for the study, but do not participate in the study, are not considered enrolled.

# 9.3. Analysis Sets

The following analysis populations have been defined for this study: Safety Population, Full Analysis Set Population (FAS), and Per Protocol (PP) Population. For this analysis, the definitions are presented in Table 7.

CONFIDENTIAL 55 27 February, 2024

**Table 7. Populations for Analysis** 

| Analysis Set                 | Description   |
|------------------------------|---|
| Safety Population            | All participants who are enrolled, and for whom study intervention is initialized under the study protocol. Participants who do not receive any amount of the study drug will still contribute to the safety analysis if study intervention was initialized but not completed, since all AEs of intervention must be assessed. All safety analyses will utilize the Safety Population.  |
| Full Analysis Set Population | All participants who receive 2 doses of study drug, and who have any post-baseline clinical assessments. The secondary efficacy analyses will be performed using data from the FAS Population.  |
| Per Protocol Population      | The subset of the FAS Population who complete 4 weeks of follow up post second dose with no major protocol deviations (including but not limited to: failure to satisfy all inclusion and exclusion criteria, failure to adhere to all protocol-required restrictions and prohibitions, receipt of prohibited concomitant procedures or therapies, and non-compliance to protocol-specific procedures) as determined by a review of participant data. The analysis of efficacy performed using data from the PP Population will be considered supportive of the FAS analysis. |

AEs=adverse events; FAS=Full Analysis Set; PP=Per Protocol

# 9.4. Statistical Analyses

The statistical analysis plan (SAP) will be finalized and approved prior to the database lock and will include a more technical and detailed description of the statistical analyses described in this section. This section is a summary of the planned statistical analyses of the most important endpoints including primary and key secondary endpoints.

#### 9.4.1. General Considerations

All descriptive statistical analyses will be performed using SAS (Version 9.4 or higher) or R (Version 3.6.2 or higher), unless otherwise noted. For categorical variables, the number and percentage within each category of the parameter will be calculated. For continuous variables, the number of participants with no missing data (n), mean, median, standard deviation (SD), minimum, and maximum values will be presented.

For the purpose of statistical analyses, a month is considered equivalent to 30 days, and a year is considered equivalent to 365 days.

# 9.4.2. Primary Endpoints (Safety)

The safety of treatment with TRP-8802, which is evaluated by vital signs (HR and BP) and AEs, is the primary endpoint. Vital signs and AEs will be collected from the Baseline (deep

CONFIDENTIAL 56 27 February, 2024

phenotyping) visit until the EOT visit (Day 64) at the time points specified in the SoA (Section 1.3).

Descriptive statistics will be used to present the count and the percentage of participants in the Safety Population who experience an AE.

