Higher doses of psilocybin (greater than 0.3 mg/kg) also may transiently lead to elevated mean BP, peaking 30 to 60 minutes following psilocybin administration and returning to baseline levels after 90 to 180 minutes without necessitating further interventions (Griffiths 2006; Hasler 2004). The severity of elevations in BP was usually asymptomatic and was graded as mild or moderate. Although several subjects in a University of Wisconsin dose-escalation study reached BP elevations that were graded as moderate, they remained asymptomatic (Brown 2017). It is not clear whether the changes in BP and HR are due to the elevated psilocin concentration directly or to the psychedelic effect caused by this active metabolite. Psilocybin appears to produce only slight sympathetic system activation (Hasler 2004; Gouzoulis-Mayfrank 1999).

Transient elevations of HR were common in subjects receiving psilocybin at doses of 0.3 mg/kg or more. The time course of these elevations in HR is similar to those seen for the elevation in BP, peaking between 60 to 120 minutes after the dose. This is similar to time of peak psilocin concentrations and peak psychedelic effect. Again, it is not clear whether or not the changes in BP and HR are directly due to the elevated psilocin concentration or caused indirectly by the psychedelic effect. In a phase 1 dose-escalation study in healthy volunteers, there were several instances in which mild bradycardia and tachycardia were noted. Psilocybin resulted in an increased HR, with slightly higher mean change from baseline in HR ( $\Delta$ HR) at higher psilocybin doses and corresponding higher psilocin exposures (Dahmane 2021). The maximum mean  $\Delta$ HR was observed at the time of psilocin maximum observed concentration (Cmax) (i.e., at 2 hours post dose) in nearly all psilocybin dose groups, and mean  $\Delta$ HR decreased with decreasing psilocin concentration at subsequent time points. Instances of bradycardia or tachycardia were unimodal, with no swing between bradycardia and tachycardia after a given dose. The episodes of bradycardia and tachycardia reported in recent studies were asymptomatic ("mild" or Grade 1) and did not require treatment (Tryp-8802 IB). Further information can be found in the current Tryp-8802 IB.

Mild headaches are common within the 24 hours after a dose of psilocybin. No auras or photo/phonophobia are associated with these headaches, which respond well to a single dose of

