## 8.1.1. Vital Signs

Heart rate and BP will be assessed before TRP-8802 capsule administration and at 30, 60, 90, 120, 180, 240, 300, and 360 minutes after capsule administration. Blood pressure and pulse measurements should be preceded by at least 5 minutes of rest for the participant in a quiet setting without distractions (e.g., television, cell phones). Blood pressure and pulse measurements will be assessed with a completely automated device. Manual techniques will be used only if an automated device is not available. If a patient's blood pressure is >200 systolic or >110 diastolic for more than 15 minutes (i.e. 4 consecutive readings) they will be transferred to ED whether or not they are symptomatic.

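### Section 9.4.2 puts heart rate and blood pressure in the primary endpoint without defining a summary for them, and reports AEs without intervals against a hypothesis that has no criterion

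*Combined protocol and SAP*

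**What the plan says.** Section 9.4.2 states: "The safety of treatment with TRP-8802, which is evaluated by vital signs (HR and BP) and AEs, is the primary endpoint". It then names one analysis: "Descriptive statistics will be used to present the count and the percentage of participants in the Safety Population who experience an AE". It gives none specific to HR or BP.

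Section 9.4.1 supplies the defaults. "For continuous variables, the number of participants with no missing data (n), mean, median, standard deviation (SD), minimum, and maximum values will be presented". "For categorical variables, the number and percentage within each category of the parameter will be calculated". Neither includes an interval.

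Section 9.1 gives the hypothesis: "it is hypothesized that oral TRP-8802 in concert with psychotherapy will be safe and well-tolerated among participants with FM". It states no rate, margin or other criterion. Section 9.2 sets the size by precedent from earlier pilot studies: "participants will be screened with the goal of enrolling approximately 10 participants who will complete both doses of TRP-8802".

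Section 8.1.1 schedules HR and BP before dosing and at 30, 60, 90, 120, 180, 240, 300 and 360 minutes after it. Its only numerical limit concerns BP (">200 systolic or >110 diastolic for more than 15 minutes") and serves as a trigger for transfer, not as an analysis category. Section 2.3 puts the BP peak at 30 to 60 minutes, and describes HR as "peaking between 60 to 120 minutes after the dose".

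**The concern.** Each session yields nine readings of each vital sign, and there are two sessions. The plan does not say what is summarised: the raw value, the change or the peak. It does not say whether the sessions are kept apart. The reference value is also open, because Section 4.1.2 treats Day 1 assessments as baseline while Section 8.1.1 takes a pre-dose reading on the day. The secondary pain endpoint in Section 9.4.3, with its 7-day windows and responder rule, is defined more closely than this part of the primary endpoint.

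For AEs, a bare percentage from about 10 people does not show how little it excludes, and nothing says which result would bear out Section 9.1. At stake is what the pilot can hand to the next study: how large the individual haemodynamic response was at each dose, and how precisely AE frequency is known.

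**Working it through.** **The plan's own figure.** The target of about 10 rests on precedent. The protocol gives no alpha, event rate, SD or precision target, so there is no calculation to reproduce. The two-sided 95% level below is my assumption.

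**AE precision at n = 10 (Clopper-Pearson).**
- 0/10: upper limit = 1 − 0.025^(1/10) = 1 − 0.692 = 0.308. Interval: 0 to 30.8%.
- 1/10: lower limit = 1 − 0.975^(1/10) = 0.0025; upper limit = 0.975 quantile of Beta(2, 9) = 0.445. Interval: 0.3% to 44.5%.
- Chance of seeing no event when the true rate is p: (1 − p)^10. At p = 5% this is 0.599; at p = 10% it is 0.349.
- Ten is the target for completers, so the Safety Population may differ. The upper limit for zero events is 36.9% at n = 8, 26.5% at n = 12 and 21.8% at n = 15 (assumed range).

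**Peak against time-point mean.** Let x_i(t) be participant i's change from pre-dose at time t. Always,

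max over t of mean_i x_i(t) ≤ mean_i [max over t of x_i(t)],

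with equality only if all participants reach their maximum at a common reading. Section 2.3's windows each contain more than one scheduled reading (30 and 60 minutes for BP; 60, 90 and 120 for HR), so peaks can fall at different readings. The direction is certain. The size cannot be derived, because the documents do not give the shape or spread of individual curves.

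**Sessions.** Dose 1 is 15 mg; Dose 2 is 25 mg, or 15 mg repeated (Sections 4.1.4 and 6.5). Section 4.3 equates 0.3 mg/kg with 23.4 mg on average, so the mean weight in that cited study was 23.4/0.3 = 78 kg. At that weight, 15 mg is 15/78 = 0.19 mg/kg and 25 mg is 25/78 = 0.32 mg/kg. Section 2.3 reports BP rises above 0.3 mg/kg and HR rises at 0.3 mg/kg or more. At that weight the two doses lie on either side of the level, so pooling sessions would mix unlike exposures.

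**Counting high readings.** The Section 8.1.1 limit needs more than 15 minutes, glossed there as four consecutive readings. Scheduled readings are at least 30 minutes apart, and four consecutive ones span at least 3 × 30 = 90 minutes. The duration condition therefore cannot be derived from them. Whether any reading exceeded 200 systolic or 110 diastolic can be. Section 8.1.1 gives no HR limit, so no matching HR count exists.

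**The case against.** A reader might infer that HR and BP have no analysis at all. The documents do not support that: Section 9.4.1 applies to every continuous variable.

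A reader might also infer that the default conceals peaks. That goes too far. No text prescribes time-point means alone, and the default includes the maximum, so any tabulated time point shows its most extreme value. What it does not show is how many participants had large rises, or each rise relative to that person's own pre-dose reading.

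High readings are partly caught elsewhere. Section 10.2.1 counts a vital-sign abnormality as an AE when the investigator judges it clinically significant, and Sections 5.5 and 10.1.5 set pause and review rules for related events. This stands, but it depends on judgment and does not summarise the measurements. The pause rules are not tied to the Section 9.1 hypothesis.

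It may be said that missing intervals are why the hypothesis cannot be judged. The missing criterion is the stronger reason; intervals alone would not settle it. Wide intervals come with any study of 10, and Section 9.2 claims only preliminary evidence. Nothing in the protocol says that 0/10 would be read as proof of safety.

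Finally, Section 9.4 calls itself a summary and leaves detail to an SAP due before database lock. That makes this a gap rather than an error. However, the same section says it covers the primary endpoint, and in an open-label study an SAP that is final only at lock allows the HR and BP summary to be chosen after the data have been seen.

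**Conclusion.** The point holds as a gap in specification, worth closing because it is cheap. HR and BP have only a generic summary that does not use the within-participant peak, separate the sessions or count participants with high readings. AE results have neither an interval nor a criterion to meet.

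The size that can be stated is the AE precision: at n = 10, no events is compatible with a true rate of up to 30.8%, and one event with 0.3% to 44.5%. This rests on a two-sided 95% level and 10 participants in the denominator. No size can be put on the difference between time-point means and individual peaks, so none is claimed.

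**What to change.** In Section 9.4.2:
- Name the same-day pre-dose reading as the reference for the dosing-session analysis.
- For each dosing session, labelled by the dose actually received, report each participant's maximum change from that reading in systolic BP, diastolic BP and HR, summarised with the Section 9.4.1 statistics. Keep time-point means beside it, because the largest of eight readings tends to lie above the pre-dose value through ordinary variation alone.
- Report the number of participants with any reading above 200 systolic or 110 diastolic. State that this is a count of readings and does not reproduce the 15-minute condition. Set no HR count unless the protocol defines a limit.
- Give exact (Clopper-Pearson) 95% intervals with AE and SAE proportions, and state the denominator.

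In Section 9.1, replace the hypothesis with an objective to estimate AE frequency, quoting the precision that about 10 participants allow.

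All of this uses data already scheduled for collection. The cost is a few extra table rows and a less strong safety statement.

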## 9.4.3. Secondary Endpoints (Efficacy)

The results of secondary endpoints will be shown at the baseline and each follow up visits based on Full Analysis Set Population and the PP Population. Pain score, pain interference, sleep disturbance, chronic pain acceptance, and the patient global impression of change were chosen as secondary measures given their relevance to FM symptom management (Clauw 2014; Williams 2011; Kratz 2007; Farrar 2001).

Aggregate worst pain score change from baseline to EOT (Day 64) will be measured on the 11-item PI-NRS. Average daily pain score will be measured from Day 1 to 7 (baseline) versus the 7 days immediately before EOT (Days 57 to 63). Changes in the worst pain intensity from the baseline through EOT will be presented in Full Analysis Set Population and the PP Population. A 30% or 2-point decrease in aggregated worst pain scores at either movement or rest will be considered a clinically significant response (Farrar 2001).

Pain interference is the degree to which pain affects important aspects of an individual's life, such as social, cognitive, and physical activities. The pain interference and its change from the baseline will be shown at the baseline and each follow up visit. Sleep disturbance includes assessment of sleep quality, perceived ability to fall and stay asleep, satisfaction of sleep, and depth of sleep. Sleep disturbance and its change from the baseline will be reported as well. In addition, chronic pain acceptance will be presented at baseline and follow up. Finally, patient impression in clinical status change will be shown.

## 9.4.4. Exploratory Endpoints (Efficacy)

Exploratory endpoints may be used for possible future investigation(s) and are further described in the SAP.

## 9.4.5. Handling of Missing Data

Every effort will be undertaken to limit premature discontinuations and ascertain completeness of data collection. All other analyses will utilize only actual participant data which is collected; no imputation of missing data will be performed unless there is > 10% of data missing.

#### 9.4.6. Subgroup Analysis

Due to small sample sizes, there no subgroup analyses are planned in this study.

## 9.5. Interim Analysis

No interim analysis is planned.

CONFIDENTIAL 57 27 February, 2024

# 10. Supporting Documentation and Operational Considerations

# 10.1. Appendix 1: Regulatory, Ethical, and Study Oversight Considerations

## 10.1.1. Regulatory and Ethical Considerations

- This study will be conducted in accordance with the protocol and with the following:
  - Consensus ethical principles derived from international guidelines including the Declaration of Helsinki and Council for International Organizations of Medical Sciences (CIOMS) International Ethical Guidelines
  - o Applicable ICH Good Clinical Practice (GCP) Guidelines
  - o Applicable laws and regulations
- The protocol, protocol amendments, ICF, TRP-8802 IB, and other relevant documents (e.g., advertisements) must be submitted to an IRB by the investigator and reviewed and approved by the IRB before the study is initiated.
- Any amendments to the protocol will require IRB approval before implementation of changes made to the study design, except for changes necessary to eliminate an immediate hazard to study participants.
- Protocols and any substantial amendments to the protocol will require health authority approval prior to initiation except for changes necessary to eliminate an immediate hazard to study participants.
- The investigator will be responsible for the following:
  - Providing written summaries of the status of the study to the IRB annually or more frequently in accordance with the requirements, policies, and procedures established by the IRB
  - Notifying the IRB of SAEs or other significant safety findings as required by IRB procedures
  - Providing oversight of the conduct of the study at the site and adherence to the IRB and all other applicable local regulations

#### 10.1.2. Financial Disclosure

Investigators and sub-investigators will provide the sponsor with sufficient, accurate financial information as requested to allow the sponsor to submit complete and accurate financial certification or disclosure statements to the appropriate regulatory authorities. Investigators are responsible for providing information on financial interests during the course of the study and for 1 year after completion of the study.

## **10.1.3. Informed Consent Process**

- The investigator or his/her representative will explain the nature of the study to the participant and answer all questions regarding the study.
- Participants must be informed that their participation is voluntary. Participants will be required to sign a statement of informed consent that meets the requirements of local regulations, ICH guidelines, HIPAA requirements, where applicable, and the IRB or study center.

CONFIDENTIAL 58 27 February, 2024

• The medical record must include a statement that written informed consent was obtained before the participant was enrolled in the study and the date the written consent was obtained. The authorized person obtaining the informed consent must also sign the ICF.

- Participants must be re-consented to the most current version of the ICF(s) during their participation in the study.
- A copy of the ICF(s) must be provided to the participant.

Participants who are rescreened are required to sign a new ICF.

#### 10.1.4. Data Protection

- Participants will be assigned a unique identifier by the sponsor. Any participant records or datasets that are transferred to the sponsor will contain the identifier only; participant names or any information which would make the participant identifiable will not be transferred. These data may be shared in this form with other research collaborators after completion of appropriate data sharing agreements via the University of Michigan.
- The participant must be informed that his/her personal study-related data will be used by the sponsor in accordance with local data protection law. The level of disclosure must also be explained to the participant who will be required to give consent for their data to be used as described in the informed consent.
- The participant must be informed that his/her medical records may be examined by Clinical Quality Assurance auditors or other authorized personnel appointed by the sponsor, by appropriate IRB members, and by inspectors from regulatory authorities.

## 10.1.5. Safety Review Committees Structure

The SRC will be responsible for the assessment of safety and to make recommendations regarding study progression. The SRC will be composed of the principal investigator, a study therapist, and a study physician. Participant safety, which includes safety signal detection at any time during the study, will be continuously monitored by the SRC. All safety data collected will be summarized and reviewed by the SRC for agreement of next steps.

In particular, data will be reviewed by the SRC if one of the following Stopping Rules is met (Section 5.5):

- one SAE considered at least possibly related to the study drug
- one Grade 3 or Grade 4 AE considered at least possibly related to the study drug
- clinically similar Grade 2 AEs considered at least possibly related to the study drug in 2 participants
- HPPD

